Psychotic disorders cause distressing symptoms and severely impact quality of life (Packer et al., 1997). Many patients with schizophrenia smoke cannabis recreationally (Hunt et al., 2018), a behaviour which is associated with negative outcomes including increased risk of relapse (Schoeler et al., 2016) and more severe psychotic symptoms (Henquet et al., 2010). The compound found in cannabis which is responsible for these effects is $\Delta 9$ -tetrahydrocannabinol (THC). Experimental studies in healthy controls have shown that pre-treatment with cannabidiol (CBD), another compound produced by the cannabis plant, can counteract THC induced psychotic symptoms and cognitive impairment without significantly modifying other subjective effects (Englund et al., 2013) (Haney et al., 2016). No previous study has investigated whether

CBD is able to moderate the effects of acute THC intoxication in individuals diagnosed with a psychotic disorder such as schizophrenia.

The present study will recruit participants with a diagnosis of schizophrenia who use cannabis regularly. Participants will attend the laboratory on three occasions: an initial visit to check that they are safe to join the study, and two experiments. On the morning of experimental visits, each participant will be administered either an oral dose of CBD (1000mg) or a matching placebo. The order of CBD/placebo administration will be randomised across the two visits. Three hours later, they will be administered a dose of vaporised cannabis containing THC. The THC cannabis administration will follow a standardised inhalation procedure using a medical-grade vaporizer device.

Once intoxicated, participants will complete a series of standard cognitive tasks as well as tasks exploring specific psychotic phenomena: the White Noise Task (Galdos et al., 2010) and the Advice Taking Task (Diaconescu et al., 2019). Finally, measures of subjective and objective psychotic phenomena as well as measures of other relevant subjective states (i.e. mood, anxiety, pleasure, hunger) will be collected.

The study will be carried out at the NIHR-Wellcome Trust Clinical Research Facility at King's College Hospital by researchers who have experience of testing cannabinoid compounds in the acute setting and working with people with psychotic disorders. All participants will be individuals who already use cannabis regularly so that they are not exposed to any additional harm. The researchers will closely monitor those taking part to make sure that they are well, both during the visits and for several weeks afterwards. The study will comply with the Declaration of Helsinki and will be conducted in the principles of Good Clinical Practice (GCP). It will be reviewed and approved by a relevant Research Ethics Committee (REC).

2 Objectives

2.1. Primary objective

To assess the extent to which, in individuals with schizophrenia, the presence of CBD attenuates the acute effects of THC on cognitive impairment and psychotic symptoms.

2.2. Secondary objectives

The secondary aims are to compare THC administration following CBD pre-treatment with placebo pre-treatment on the following outcomes:

1. Cognition (including verbal learning, delayed recall, working memory)
2. Psychotic symptoms (positive and negative)
3. Specific psychotic phenomena (auditory hallucinations, persecutory beliefs)
4. Anxiety
5. Other subjective experiences
6. THC, CBD and metabolite plasma levels
7. Plasma endocannabinoid levels and potential biomarkers and inflammatory markers

3 Trial Design

3.1 Trial Design

Randomised, double-blind, placebo-controlled, two-arm, cross-over, within-subjects study.

The study includes one baseline visit followed by two experimental visits, separated by at least one week.

3.2 Study Flowchart

	Initial Brief Screening	Baseline Visit	Experimental Visits 1 & 2
Informed consent		x	
Physical examination		x	
Demographic and clinical information	x	x	
Physical Observations		x	x
Alcohol, Drug and Pregnancy Tests		x	x
Blood sampling		x (antipsychotic level only)	x
Cannula			x
CBD/placebo administration			x
THC administration			x
Cognitive and psychopathological testing		x	x
Sobriety test			x
Follow-up call (+ 1 day)			x
Follow-up call (+7-10 days)			x

3.3 Recruitment

The research team will contact local clinical services (ie. inpatient wards and community mental health teams (CMHTs)) and ask them to identify patients who are likely to meet the study's inclusion

criteria. Clinicians will then ask potential participants if they agree to be contacted by the study team. The researchers will also utilise the South London and Maudsley NHS Foundation Trust (SLaM) Consent for Contact initiative in order to recruit Trust patients and will follow the related Trust policy. The researchers will then contact potential participants by telephone or in person to explore their eligibility for the study and answering any questions they have about what participation in the study entails. The researchers will also obtain consent from the participant for the research team to review their clinical notes and discuss their history with their clinical team. If the participants' responses to the initial questions are satisfactory, and there are no issues identified from the review of their clinical notes or discussion with the clinical team, the participant will be invited for a Baseline visit and be provided with a Participant Information Sheet (PIS).

3.1 Inclusion Criteria

Each participant must meet **ALL** of the following criteria:

- i. Age 18-65 years
- ii. Clinical diagnosis of schizophrenia or schizoaffective disorder (i.e. documented as such in the patient's clinical records and satisfying ICD-10 criteria for F20 or F25)
- iii. Clinically stable for at least three months (since discharge from hospital, home treatment team, or prior clinical deterioration, and with agreement from the patient's responsible clinician)
- iv. Regular (at least weekly) cannabis use for the past 3 months or more
- v. Evidence from either clinicians or from the patient that cannabis use exacerbates their symptoms or increases their risk of relapse
- vi. Treatment with regular doses of antipsychotic medication for at least 1 month, confirmed by a blood test at the baseline visit if the participant is not prescribed an injectable formulation, and with the participant agreeing to be maintained at a stable dose over the course of the experiment
- vii. The participant agrees to abstain from cannabis use for at least 24 hours prior to study visits
- viii. The participant is willing to have an intravenous cannula inserted to collect blood samples on experimental visits
- ix. Sufficiently fluent English
- x. Providing written informed consent

3.3.2 Exclusion Criteria

If the participants **ONE OR MORE** of the following criteria they will be excluded from the study:

- i. Extreme cannabis use, participant is estimated to be using over 2 grams of cannabis/day
- ii. Dependence on alcohol or illicit substances (other than cannabis) as defined by ICD-10
- iii. Pregnancy (current or planned) or breastfeeding
- iv. Physical health disorder or another mental health disorder that the study psychiatrist judges may influence the patient's ability to tolerate the procedure, or that may alter the results of the study.
- v. The participant has taken part in any drug study within the last 3 months or taking part in another study over the course of the trial
- vi. Drug sensitivity/allergy to cannabis or Lorazepam
- vii. Unlikely to be able to complete the series of procedures and study sessions for any reason, as judged by the study psychiatrist

3.3.3 Withdrawal of Subjects

Participants are free to withdraw from the study at any stage for any reason. The researchers may withdraw the participant from the study up until they complete their final experimental visit if it becomes apparent that they do not meet all inclusion and exclusion criteria. The researchers may also withdraw the participant due to adverse or serious adverse effects, protocol violations, administrative or other reasons.

The researchers will ask the participant why they have decided to withdraw and will explain that this data will be recorded anonymously. The participant will not be obliged to disclose their reasons for withdrawal. The participant will be able to withdraw their data until two weeks after the final study visit but will not be able to withdraw their data after this point.

3.4 Baseline visit

3.4.1 Consent

The baseline visit will be held at either the participant's CMHT or at the King's Clinical Research Facility (CRF). At the start of the visit the researchers will explain to the participant the aims and procedures of the study once more. The participant will be given time to re-read the PIS and to ask questions about the study. The participant will be informed about what will happen during the rest of baseline visit and experimental sessions including requirements regarding alcohol and other drug use during and between study visits as well as data protection and confidentiality issues. If consenting, the participant and researcher will then read and sign the consent form.

3.4.2 Assessment for Study Eligibility

To assess for eligibility the following assessments will be completed by the study psychiatrist:

- i. Mini-International Neuropsychiatric Interview to screen for co-morbid (non-schizophrenia) mental illness
- ii. Clinical interview covering medical, psychiatric and substance use histories
- iii. Review of electronic health records (electronic Patient Journey System)
- iv. Discussion with the participant's Responsible Clinician
- v. Mental state examination
- vi. A targeted physical examination depending on physical co-morbidities identified during the assessment

3.4.3 Collection of additional demographic and clinical information

The following information will also be collected through interview of the participant and assessment of their electronic health records:

- i. Demographics: age, gender, ethnicity, education level, employment, marital status
- ii. Clinical information
 - a. Current and past diagnosed psychiatric and medical illnesses
 - b. Current and past substance use
 - c. Current and past prescribed medications including long-acting injectable formulations and clozapine

- d. Admissions to psychiatric hospital, their legal status under the Mental Health Act, their duration, and admission to psychiatric intensive care wards
- e. History of being subject to a Community Treatment Order
- f. Management by forensic mental health services
- g. Custodial/prison sentences
- h. Health of the Nation Outcomes Scale score (most recent)

- iii. Cannabis-Experiences Questionnaire (CEQ). A questionnaire concerned with subjective experiences of cannabis (Barkus et al., 2006). It has 13 questions divided into three subscales: Pleasurable Experiences, Psychosis-Like Experiences and After-Effects.
- iv. Timeline Follow-back (Cannabis). This questionnaire obtains a variety of quantitative estimates of substance use.
- v. The Cannabis Use Disorder Identification Test – Revised (CUDIT-R) (Adamson 2010)
- vi. Substance Use Awareness and Insight Scale (SAS) (Kim 2021)
- vii. Psychotomimetic States Inventory (PSI). A 48-item questionnaire that measures psychotic-like experiences. The PSI was developed for use in drug studies, particularly cannabis and ketamine studies (Mason et al., 2008). Items are rated on a 4-point scale (from 0 = never to 3 = strongly). The PSI has subscales of delusionary thinking, perceptual disorders, cognitive disorganisation
- viii. Drug Use Disorders Identification Test (DUDIT). An 11-item self-administered screening instrument for drug-related problems.
- ix. Alcohol Use Disorders Identification Test (AUDIT). 10 question alcohol harm screening tool.
- x. Wechsler Test of Adult Reading (WTAR). This tool is used to provide a measure of premorbid intelligence (Wechsler, 2001).
- xi. Revised-Green Paranoid Thoughts Scale. A scale which comprises an eight-item ideas of reference and 10-item ideas of persecution subscale (Freeman et al., 2019).
- xii. State Trait Anxiety Scale. This scale differentiates between the temporary condition of "state anxiety" and the more general and long-standing quality of "trait anxiety." The trait scale will also be used as an outcome measure (Spielberger 1983).
- xiii. Carbon monoxide breath test. This test uses a simple handheld device. Carbon monoxide levels can be used as a measure of nicotine dependence.
- xiv. Height, weight, body mass index, body fat content (%).

3.4.4 Assessment for eligibility to continue with baseline and experimental visits

As well as meeting the study's inclusion and exclusion criteria, participants must fulfil a number of additional criteria at the baseline and experimental visits before completing any outcome measures.

If a participant does not meet these criteria the visit will be postponed. Depending on the individual circumstances, the investigators will consider whether failing these criteria will mean that a participant has to be withdrawn from the study.

- i. Negative alcohol breath test
- ii. Negative urine drug screen (apart from cannabis and prescribed medication)
- iii. Negative urine pregnancy test
- iv. Stable mental state, as judged by the investigator and in light of the participant's normal baseline symptomatology

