To assess the extent to which, in individuals with schizophrenia, the presence of CBD attenuates the acute effects of THC on cognitive impairment and psychotic symptoms.

Primary hypotheses and outcome measures

Hypothesis 1: CBD will reduce the impairment in delayed verbal recall compared with placebo.

Outcome measure: Hopkins verbal learning task – delayed verbal recall. The total number of words correctly recalled at 20-25 minutes.

Hypothesis 2: CBD will reduce the severity of positive psychotic symptoms compared with placebo.

Outcome measure: Positive and Negative Syndrome Scale (PANSS) - Positive subscale. Change from pre-CBD/placebo to post-THC.

Secondary hypotheses and outcome measures

Hypothesis 3: CBD will reduce state anxiety compared with placebo.

Outcome measure: State-Trait Anxiety Inventory (STAI-S). Change from pre-CBD/placebo to post-THC.

Hypothesis 4: CBD will reduce the impairment in working memory compared with placebo.

Outcome measure: Forward and reverse digit span. The total number of numbers correctly repeated.

Data processing and statistical analysis

Data processing and missing data

Multiple imputation chain equations (MICE) will be used to impute missing values in psychopathological, cognitive, physiological, and pharmacokinetic outcomes using the mice package in R. We will complete sensitivity analyses to assess the effect of data imputation.

Analysis population

Primary analyses will be per-protocol (i.e. data where participants completed a pair of experiments). For participants who completed more than one pair of experiments, the data from the experiments where the highest THC dose was administered will be used. We will complete sensitivity analyses i) using the data from all participants who completed pairs of experiments with 20mg THC; and ii) intention to treat analyses.

Order effects

It will be assumed that there are no carryover effects from the previous experimental session as there was sufficient time for drug washout between session. A period effect may be present due to learning and because participants become more comfortable with the lab environment over time. We will therefore include visit number in all models to account for potential order effects.

Correction for multiple comparisons

Benjamini Hochberg correction will be conducted across outcomes locally i.e. across secondary cognitive outcomes, secondary psychopathological outcomes, visual analogue scales and physiological outcomes.

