3.6.2 Blood and urine collection, handling and analysis

Urine will be tested using a bedside drug screen and a bedside pregnancy test. One urine sample, collected at the screening or baseline visit will be stored for laboratory analysis of cannabinoids. Urine samples will be decanted into screw-cap collection tubes and be placed in a -20°C freezer and then -80°C freezer as soon as possible. The stored samples will be anonymised with participant ID, visit number and time point of collection and freezing. Samples will be analysed and processed according to standard procedures. All other urine samples will be disposed of immediately.

At the baseline visit, a blood sample will be taken to test for prescribed antipsychotic levels. The test will be completed by ViaPath and be processed according to standard clinical procedures.

On experimental visits, participants will have a venous cannula inserted for collection of blood samples. Blood samples will be taken before administration of CBD/placebo, 1.5 hours post CBD administration (30mins pre-THC inhalation) and at 0, 5, 15 and 90 minutes after the end of the THC/placebo inhalation procedure. Each sample will be collected in a 5ml EDTA tube (green). Within 10min of collection, the samples will be centrifuged (3000rpm for 10 minutes). The plasma will be decanted from the EDTA tube into two screw-cap collection tubes and immediately placed in a -20°C freezer. The stored samples will be anonymised with participant ID, visit number and time point. Only the research team will be able to link ID number to participant details. The samples will be moved to a -80°C freezer for longer term storage as soon as possible. Only plasma will be stored so that analyses can be completed. No human tissue will be stored at the end of the research, all

tissues will have been disposed of in accordance with the Human Tissue Authority's Code of Practice

Plasma samples will later be analysed for the levels of prescribed antipsychotic, Δ9-THC, 11-OH-Δ9-THC, 11-COOH-Δ9-THC, CBD, 6-OH-CBD and 7-OH-CBD, potential biomarkers and inflammatory markers using high performance liquid chromatography–mass spectrometry at King's College Hospital and at the University of Turku, Finland.

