5.1 Sample Size

The relative effects of THC and CBD/THC have never been compared in this population previously. We chose a sample size (n=30) which we believe has adequate power to detect meaningful effects. In a two-tailed paired sample t-test, a sample size of n=30 has 80% power, at alpha=0.05 to detect an effect size of 0.53. In a study comparing the effect of THC relative to CBD/THC on psychotic symptoms in healthy volunteers[27], the effect size for increase in State Social Paranoia Scale was d=0.64. Assuming a drop-out rate of 25% (as in previous studies using this methodology), we plan to initially enrol n=40 patients.

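### 24-hour cannabis abstinence and CBD washout are taken on trust, although pre-dose plasma already collected could check both indirectly and sharpen the THC exposure comparison

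*Combined protocol and SAP*

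**What the plan says.** **Abstinence.** Inclusion criterion vii reads "The participant agrees to abstain from cannabis use for at least 24 hours prior to study visits", and protocol 3.5.2 asks for the same before experimental visits. Section 3.4.4 lists what must be met on the day: an alcohol breath test, a "Negative urine drug screen (apart from cannabis and prescribed medication", a pregnancy test and a stable mental state. Timeline Follow-back and the carbon monoxide test appear only among the baseline data (3.4.3).

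**Washout.** Protocol 3.5 (Experimental visits) sets a minimum gap of one week. The SAP, under Order effects, states "It will be assumed that there are no carryover effects from the previous experimental session as there was sufficient time for drug washout". The documents give time to peak and bioavailability for CBD, but no elimination figure.

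**Available data.** Protocol 3.6.2: "Blood samples will be taken before administration of CBD/placebo". The timetable calls this blood sampling I. The plasma is assayed later for THC, its metabolites, CBD and CBD metabolites.

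**Planned use.** The SAP summarises pharmacokinetics descriptively and compares THC and metabolite Cmax and AUC between arms with an unadjusted two-condition test. The efficacy models contain treatment, visit number and participant. The sensitivity analyses concern imputation, the 20 mg pairs and intention to treat. None uses the pre-dose level.

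**The concern.** A regular user who smoked on the morning of a visit passes the urine criterion and can proceed if judged stable. The addendum puts mean use at 1 g a day, about 150 mg THC, against a 20 mg starting dose; eligibility extends to 2 g, about 300 mg. If recent use differs between the two visits of a pair, two things follow.

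- THC already in plasma enters the Cmax and AUC being compared. It is noise in the analysis that tells the reader whether CBD changes THC exposure.
- Delayed recall and digit span are raw post-THC scores with no same-visit pre-dose score, so a visit-specific shift goes straight into the paired difference. The addendum itself cites frequent users whose delayed recall improved slightly on THC and attributes this to withdrawal under placebo. The protocol therefore accepts that recent-use state can move a primary outcome.

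Residual CBD is a separate matter. At a placebo visit that follows a CBD visit it would pull the CBD-placebo difference towards zero, and a null result would be harder to read.

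**Working it through.** **1. The plan's own figure.** Protocol 5.1: "In a two-tailed paired sample t-test, a sample size of n=30 has 80% power, at alpha=0.05 to detect an effect size of 0.53". Paired t-test, noncentral t, df = 29, noncentrality 0.53 × √30 = 2.90: power 80.1%. With a period term (df = 28) it is 80.0%. The figure reproduces, and at d = 0.53 it leaves almost no reserve. At the cited healthy-volunteer value ("the effect size for increase in State Social Paranoia Scale was d=0.64") power would be 92.3%.

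**2. Unequal recent use (assumed inputs).** Let a share p of visits breach abstinence independently, each breach shifting the outcome by δ SDs of the paired difference. Added variance is 2p(1−p)δ², and effective d is 0.53/√(1 + added variance).

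| p | δ | Added variance | Effective d | Power, n=30 |
|---|---|---|---|---|
| 0.1 | 0.4 | 2 × 0.09 × 0.16 = 0.029 | 0.523 | 79.0% |
| 0.3 | 0.8 | 2 × 0.21 × 0.64 = 0.269 | 0.471 | 70.2% |

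**3. Residual CBD (assumed half-lives, effect proportional to level).** The fraction left after D days is r = 0.5^(D/half-life). Only placebo visits after CBD are affected. With half the participants CBD-first, the estimate is d(1 − r/2).

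| Half-life | r, day 7 | Shrinkage r/2 | Power, day 7 | Power, day 14 |
|---|---|---|---|---|
| 1 day | 0.8% | 0.4% | 79.8% | 80.1% |
| 2 days | 8.8% | 4.4% | 76.5% | 79.8% |
| 3 days | 19.8% | 9.9% | 71.5% | 78.5% |

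Day 7 is the minimum gap, so its column is the worst case for each half-life.

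**4. Which outcomes are exposed.** PANSS and STAI-S are changes from the same visit's pre-CBD/placebo score, so a stable shift already present at that score partly cancels. Delayed recall, digit span and the THC/metabolite parameters have no such correction.

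**5. Would deleting pairs with measurable CBD work?** Within a first pair, carryover can appear only where placebo follows CBD, so deletion removes only CBD-first pairs. With SD 1 for the paired difference, the period-adjusted SE is ½√(1/n₁ + 1/n₂), and df = n₁ + n₂ − 2. Keep 15 placebo-first pairs:

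| CBD-first pairs left | SE | Ratio to full | Power at d=0.53 |
|---|---|---|---|
| 15 | 0.183 | 1.00 | 80% |
| 8 | 0.219 | 1.20 | 64% |
| 5 | 0.258 | 1.41 | 49% |
| 3 | 0.316 | 1.73 | 35% |

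With none left, treatment and visit number cannot be separated, and the SAP expects a period effect.

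**The case against.** Much of the case on the other side stands.

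- **The levels are indirect.** A reader might infer that sample I shows who broke the 24-hour rule or who still carries study CBD. The documents give no link between plasma THC and hours since last use, and the level may also reflect habitual intake. The protocol's summary describes CBD as a constituent of the cannabis plant, so measurable CBD can come from a participant's own use.
- **The covariate is not clean.** A reader might want pre-dose THC in the primary model because it precedes that visit's dose. In a two-visit crossover, sample I at the second visit comes after the sequence is allocated and after the first treatment. If that treatment changed later cannabis use, the covariate is itself affected. A single slope would also mix differences between heavier and lighter users with a change in one person between visits. The covariate belongs in a sensitivity analysis.
- **The urine exemption is not itself an error.** In regular users a positive cannabis screen need not isolate the last 24 hours; the sub-study criteria (protocol section 4) pair a positive dipstick with self-reported use within seven days. The samples are also frozen and assayed later, so they can serve the analysis but not a decision on the day.
- **The sizes are assumed.** The lower ends of both ranges are trivial.

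None of this answers the THC/metabolite comparison. There the pre-dose amount is part of what is measured, whatever its source, and leaving it unadjusted gains nothing.

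**Conclusion.** The point holds as a cheap improvement. The plan checks neither abstinence nor washout and makes no use of pre-dose levels that will be available for both. The gain is clearest for THC and metabolite AUC and Cmax, and next for delayed recall and digit span.

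The power ranges (70-79% for recent use; 71-80% for residual CBD at day 7) depend entirely on assumed breach rates, outcome shifts and half-lives, and on effect being proportional to level. A reader might infer that carryover is present or that the trial is underpowered. The documents show neither: washout is provided for by a minimum gap and is simply not verified, and the n=30 and 80% figures are correct as stated.

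**What to change.** All three changes are in the SAP. Visit criteria and the gap between visits are not touched.

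1. **THC and metabolite AUC and Cmax.** Replace the unadjusted test with a mixed model on the log scale: treatment, visit number, participant, and that visit's log sample-I level of the same analyte. State how values below the quantification limit are handled.
2. **Delayed recall and digit span.** Keep the efficacy model as written. Add a sensitivity analysis with the within-participant deviation in log sample-I THC, entering the participant mean as a separate term. Report it beside the unadjusted result, and say that sample I at later visits follows earlier treatment.
3. **Carryover.** Replace the bare assumption with a report of sample-I CBD by visit and sequence. Compare visits after CBD with first visits (background from own use) and with the same participant's post-dose CBD level. Fix before unblinding what share of the post-dose level counts as negligible. If it is exceeded, qualify the conclusion as possibly diluted towards zero. Do not delete pairs with measurable CBD.

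Cost: one or two degrees of freedom per adjusted model and a little extra analysis. No new samples, assays or visits are needed.
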